3.6 Proposed sample size and design

Two interventions are intended to increase the response to the initial screening invitation; a pre-leaflet and online booking. These will be tested in a two factor factorial cluster randomised trial. Outcome will be attendance for a cervical screening test at 3 months, 12 months and 30 months after their 25th birthday. Adoption of a factorial design in which any one intervention is balanced for other interventions means the effect of any one intervention can be assessed independently of others provided there is no interaction on the scale of measurement.

Without a factorial design, to detect an interaction of the same magnitude, for example that the treatments are no better in combination as separately, would require an approximately fourfold increase in sample size. In phase I of this study the pre-leaflet and on-line booking are being tested in a factorial design, but only for the Manchester sample. There is unlikely to be a substantive interaction between these interventions, and so it would be difficult to justify the additional sample size required for this to be investigated. It will nevertheless be possible to check the robustness of the evaluation of the pre-leaflet intervention by comparison of effect in Manchester with that found in Salford & Trafford. In phase 2 of this study a factorial design was not chosen as we believe there is a possibility of interaction between the interventions being compared when used in combination.

Two interventions to improve response following non-attendance after 6 months will be tested, separately and in combination, with outcome being attendance at 12 months and 30 months post first call.

3.7 Randomisation methods

The screening uptake rate in the target age group, the uptake rate after a reminder and the screening uptake rate overall in the year prior to the study are likely to be strong predictors of the trial outcome measures. Data for the year prior to the trial will be extracted from the Exeter system to estimate these rates for each practice. These rates will then be used to balance the characteristics of treatment groups. To do this, the procedure described by Butler and Raab [11] will be adapted for the complex factorial design of this trial. Where practices have formed or merged the baseline uptake rates required for the minimization will be imputed using characteristics of the practice such as size and location or data from the constituent practices. A sample of allocations that give good balance between the 4 intervention factors will be identified using stochastic methods. An allocation will then be randomly selected from the sample of good allocations. This procedure will be stratified by PCT and carried out with the names and location of the practices concealed.

3.8 User Involvement

We have approached Jo's Cervical Cancer Trust (www.jostrust.org.uk) who take an active interest in cervical screening and are happy to support our proposed project. This project outline and a lay description of the project have been reviewed by young women who are members of the charity. Although the women who are members of Jo's Cervical Cancer Trust have all been affected by Cervical Cancer or Cervical Intraepithelial Neoplasia they are also women who may or may not have previously attended for cervical screening. Feedback from some of Jo's Cervical Cancer Trust's panel of women both endorsed the importance of research and our proposed strategies, including the new leaflet aimed at improving engagement with screening.

A project consultation questionnaire was also completed by 26 women, including a proportion of ethnic minorities, aged 20-25 at an inner city GP surgery in Manchester. Overall, the women were very supportive of the research. The majority of women surveyed agreed that each of the interventions would be an improvement. Views were sought from each woman regarding the proposed interventions, and the results support the interventions we are proposing. A large majority supported the idea of the pre-leaflet prior to the routine invitation. All had internet access, with half expressing a preference to book online and most of those believing it would be easier than phoning the GP. A large majority would be prepared to attend a family planning clinic for a cytology sample but half expressed a preference for their GP. Pre-booked appointments (PBA) evoked a positive response in a large majority and most of these women said that they would rearrange if the PBA was not convenient. Around 40% said they would prefer a self test for HPV and if positive would attend for a cytology sample. Finally, all of the women felt that nurse support would be beneficial, with phone contact being the most popular means of communication. This consultation with potential users makes us feel confident that different options suit different women and all of our options were viewed positively by at least a sizeable proportion of those consulted.

It is anticipated that members of Jo's Cervical Cancer trust and young women, including ethnic minorities, recruited locally will form a panel of user representatives who will advise the trial management group throughout the duration of the project. Their remit is likely to involve reviewing the patient information leaflets and letters used as part of the trial and retrospectively reviewing the advice given by the nurse navigator to ensure that this is not overly 'medicalised'. We would obtain translated versions as required for ethnic minorities. The logistics of running the panel will be decided by the women involved; Jo's Cervical Cancer Trust provides both face to face and internet based support, women may wish to offer advice to the investigators via email, however if they felt it was appropriate to have biannual or annual meetings the volunteers would be reimbursed for any travelling expenses they incurred. The panel would also be asked to elect a user representative to serve as a member of the Trial Steering Committee.

Women volunteering to serve as a member of the user representative panel will be provided with training by the trial team to provide them with the knowledge required to offer advice to the trial management group and review both the patient information and the nurse navigator's responses. It is likely that this will involve training on the purpose of cervical screening, the conduct of randomised controlled trials and an introduction to qualitative and quantitative research skills.

4. Selection and withdrawal of subjects

4.1 Planned inclusion criteria

Women aged 24 years and 6 months who are due to receive an invitation for cervical screening will be eligible to receive the pre-leaflet. Women living in Manchester PCT will be eligible for the internet booking intervention but not those from Salford, Trafford or Aberdeen. Women aged 25 years and 6 months in NW England (and 20 years and 6 months in Aberdeen) who do not have a test recorded on the Exeter system will be eligible for the nurse navigator, HPV self sampling and timed appointments interventions.

4.2 Planned exclusion criteria

Women who are not aged 25 and receiving their first invitation for screening will not be eligible for inclusion in the study. Of those women aged 25 and receiving their first invitation the following groups will be excluded:

- Women who are pregnant and have advised their GP (and consequently the screening agency) that they wish to defer their call until 3 months post delivery.
- Women who do not have a cervix and have been ceased on the screening system.
- Women who have informed their GP (and consequently the screening agency) that they have made an informed decision not to participate in this screening round.

4.3 Withdrawing participants

Should any participant that had consented to their personal details and screening attendance being recorded express a wish to withdraw at any stage of the trial, any information collected from them until that point would be retained in the trial database but no further follow up data would be collected. Retaining data will be important in the HPV self sampling cohort in order to maintain a record of the results of HPV testing. Participants will not be contacted further after they have withdrawn from the trial. Should any participant lose the ability to consent whilst the trial is ongoing, any screening attendance which has already been recorded will remain within the dataset, however further follow up data will not be collected.

5. Statistics

5.1 Sample size

5.1.1 Phase 1

Please note the following phase 1 power calculations are subsequent to the latest practice number information, for a priori calculations see earlier versions of the study protocol.

The pre-leaflet will be tested across Manchester, Salford and Trafford PCTs, which have respectively 100, 55 and 46 general practices (the total of general practices had altered by July 2013, the current totals are 97, 47 and 36, [12] with an average practice size of 4,900 patients conservatively suggesting that approximately 40 women per GP practice would become eligible for the screening programme over a 12 month period. Data from Manchester PCT suggest that the initial response to the first invitation is fewer than 30%.

The power of a cluster randomised trial designed depends on the Intra-Cluster Correlation (ICC), the number of clusters, the cluster sizes and variation in cluster size. Jensen et al suggest an ICC for a similar outcome of 0.026.[13]

Pre-leaflet intervention: With 92 practices randomised to pre-leaflet (leaflet sent to around 4000 women) and 88 control practices, the trial will have a power of 89% to detect a 5% improvement of attendance assuming an ICC of 0.026 and an average cluster size of 40.

On-line booking intervention: The online booking intervention will be tested in Manchester PCT only. With 49 practices randomised to on-line booking and 48 to control, the trial will have a power of 93% to detect a 7.5% improvement in attendance by 3 months assuming an ICC of 0.026 and an average cluster size of 40. Given that the on-line booking intervention is introduced on a different occasion to the pre-leaflet we feel that any interaction between the two interventions is unlikely so that a factorial design is justified.

Phase 2 of this study is designed to improve uptake amongst women who have not attended at 6 months. Given that entry into phase 2 depends on the outcome of phase 1, any effect of the intervention in phase 2 will bias estimates of the long term effects of the interventions in phase 1. For example the interventions in phase 2 could, at least in theory, remove any effect of the phase 1 interventions. Whilst this could be addressed through statistical analysis we plan to have a larger control group for the phase 2 interventions. Of the 180 practices 111 will receive an intervention in phase 2 of the study whilst 69 will receive no further intervention.

The effect of online booking may be cumulative over the follow-up period as access to online booking would continue to be available. 63 Greater Manchester practices will receive no intervention. These will have a power of 94% to detect a 10% increase due to access to online booking.

A modified pre-leaflet will be tested in women who have been offered HPV vaccination as part of the catch-up component of the Scottish vaccination programme (Aberdeen Cohort). The primary outcome would be the absolute increase in screening uptake by 3, 12 and 30 months compared to control. Due to the potential adverse effect of vaccination on attendance a larger intervention effect is to be expected. With an ICC of 2.6%, 38 intervention and 39 control practices (leaflet sent to 1520 women) the trial will have a power >95% to detect a 10% increase in attendance.

Figure 1 **Phase 1**

		Pre-leaflet	Pre-leaflet Control	Total
Manchester	Online Booking	24	25	49
	Online Booking Control	24	24	48
Salford		26	21	47
Trafford		18	18	36
Total (NW)		92	88	180
Aberdeen		38	40	78

5.1.2 Phase 2

The standard first reminder may increase response by 5%. At 6 months (second reminder) we estimate that at least 50% will not have attended, that is a mean of 20 women per practice. In part 2 of the study the following 5 interventions will be tested (i) self-test offered (ii) self-test sent, (iii) nurse navigator, (iv) choice between nurse navigator & self-test offered (v) timed appointments. Statistical analysis will compare each intervention as compared to control.

We might assume that a further 5% attend without further intervention by the time of next recall, and that a follow-up intervention increases uptake by an additional 5%. Amongst the 50% of women that we estimate will not have attended by 6 months this corresponds to a difference between 10% to 20%. A study with 30 practices in each of the five intervention arms (self-sample, nurse navigator, timed appointments, nurse navigator or self-sample) and 100 control practices would have a power of greater than 80% to detect this difference provided the ICC does not exceed 0.07. This calculation includes a

bonferroni correction of the significance level to allow for 5 comparisons with the control and an allowance for additional variation in cluster sizes due to the effect of stage/part 1 intervention.

Self test kits will be sent by the trial centre. About 600 self test kits will be sent out. So that the acceptability of the two kit can be compared, women will be randomised to receive either kit types using randomisation stratified by site with a random block size of 4,6 or 8. In each study site the screening centre will assign kits in order according to a pre-prepared list.

Figure 2 Phase 2

	Pre Leaflet	Online Booking	Self Test Sent	Self Test Offered	Nurse Nav	Nurse Nav + Offered	Timed appointment	Control	Total
Manchester	Yes	Yes	3	4	3	4	2	8	24
	Yes	No	3	3	4	3	2	9	24
	No	Yes	4	3	3	3	3	9	25
	No	No	2	3	2	3	4	10	24
Salford &	Yes	-	6	5	6	6	5	16	44
Trafford	No	-	4	5	4	4	5	17	39
Aberdeen	Yes	-	4	5	6	3	5	15	38
	No	-	5	6	5	5	6	13	40
Total			31	34	33	31	32	97	258

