3.3 Planned Interventions

3.3.1 Pre-call cervical screening information leaflet (pre-leaflet)

Women in England aged 24 and a half years will be sent a bespoke information leaflet around six weeks prior to their first invitation. The content of this leaflet has been informed by focus groups and consultation exercises with women aged around 24 in Manchester and 19 in Aberdeen. The rationale will be to convert them from ‘pre-contemplators’ to ‘contemplators’ (based on the Transtheoretical model) by the time the standard NHSCSP invitation is received. This will deal with key themes and issues that emerged from the focus group and consultation work which has already been completed. Leaflets produced for use with the Aberdeen cohort will be sent to young women aged 19 years who are deciding whether to accept their invitation for cervical screening. They will have recently been offered HPV vaccination and the leaflet should be equally applicable to vaccinated women in England when they begin to receive their invitations 5 years from now.

In Manchester and Aberdeen the pre-leaflet will be sent to eligible women (i.e. those aged 24 and a half or 19 and a half) in randomised practices. This will be facilitated by the local screening agencies who maintain the population based register for the cervical screening programme and routinely have access to women’s details.

The outcome of this intervention will be the proportions of women screened in the intervention and control practices measured primarily at 2-3 months, prior to the first reminder and secondarily at 12 month. These data will be provided by the local screening agencies who routinely monitor the screening uptake in the practices within the boundaries of the Primary Care Trusts for which they are responsible. The screening agency will create an anonymised record for each woman involved in the trial using a unique identifier.

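### The set of practices for long-term phase 1 effects is inconsistent, the online-booking power rests on 63 practices where Figure 2 leaves 36, and restricting to practices without phase 2 costs far more precision than the roughly 7% dilution it avoids

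*Protocol*

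**What the plan says.** Section 5.1.1 of the protocol states that "any effect of the intervention in phase 2 will bias estimates of the long term effects of the interventions in phase 1", and adds that phase 2 could in theory remove a phase 1 effect altogether. It does not say how large the bias might be. The remedy is one of design: "Whilst this could be addressed through statistical analysis we plan to have a larger control group for the phase 2 interventions". The resulting split is: "Of the 180 practices 111 will receive an intervention in phase 2 of the study whilst 69 will receive no further intervention".

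The documents then differ on which practices carry the long-term phase 1 results:

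- **Online booking.** Section 5.1.1 counts 63 Greater Manchester practices without intervention and gives those practices 94% power for a 10-point increase. The same section says online booking is tested in Manchester PCT only.
- **Leaflet, North West.** Section 3.3.1 has the proportions screened in intervention and control practices "measured primarily at 2-3 months, prior to the first reminder and secondarily at 12 month", with no restriction.
- **Leaflet, Aberdeen.** Section 5.1.1 powers the 3-, 12- and 30-month outcome on 38 and 39 practices. Figure 2 leaves only 15 + 13 = 28 Aberdeen practices without phase 2.
- **Model.** Section 5.2 sets no restriction and does not mention phase 2 arm when phase 1 effects are estimated.

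On timing, section 3.5 lists 3, 12 and 30 months. Section 3.3.2 gives online booking a 5-month measure, before the second reminder. The leaflet has no counterpart.

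**The concern.** Phase 2 arms were allocated across the phase 1 groups, as Figure 2 shows. The general principle is in section 3.6, conditional on the absence of interaction: a layout where "any one intervention is balanced for other interventions means the effect of any one intervention can be assessed independently of others". With phase 2 spread over both phase 1 groups, it mainly shrinks the phase 1 contrast and hardly confounds it. Whether to restrict is therefore a trade of bias against precision, and the protocol makes it without sizing either side.

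The later time points matter. Attendance at 3 months cannot separate a leaflet that brings attendance forward from one that adds attenders. If the later comparison is confined to a minority of practices, a lasting effect is likely to be missed. And if the set is not fixed, it can be chosen after the results are seen.

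**Working it through.** **Inputs.** 40 women per practice and ICC 0.026 (section 5.1.1). At 6 months, "At 6 months (second reminder) we estimate that at least 50% will not have attended, that is a mean of 20 women per practice"; later uptake among those women is 10% without and 20% with a phase 2 intervention (section 5.1.2). Practice counts come from Figures 1 and 2. Assumptions: two-sided 5% (not stated for phase 1), equal cluster sizes, the same conversion rates in both phase 1 groups, and the 10% and 20%, which the protocol gives for the time of next recall, used for the later time points generally.

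**Reproducing the stated powers.** Design effect = 1 + 39 × 0.026 = 2.014; effective n = practices × 40 / 2.014.

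- Leaflet, 92 v 88, 30% v 35%: 0.891 (stated 89%).
- Online booking, 49 v 48, 30% v 37.5%: 0.936 (stated 93%).
- 63 practices split 31/32, 10 points, control rate 40-50%: 0.943-0.946 (stated 94%).

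The method therefore matches the protocol's.

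**Practices without phase 2 (Figure 2).** Leaflet 8 + 9 + 16 = 33; no leaflet 9 + 10 + 17 = 36; total 69. Manchester only: online 8 + 9 = 17; no online 9 + 10 = 19; total 36.

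**Dilution.** If phase 1 adds d points by 6 months, the later effect is d(1 − 0.10) = 0.900d without phase 2 and d(1 − 0.20) = 0.800d with it. Over all 180 practices it is d[(69 × 0.900 + 111 × 0.800)/180] = 0.838d. Dilution = 1 − 0.838/0.900 = 6.9%. For d = 5 this is 4.5 against 4.19 points, a loss of 0.3 points. With phase 2 conversion of 15% to 30% in place of 20%, dilution is 3% to 14%.

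**Imbalance.** Phase 2 reaches 92 − 33 = 59 of 92 leaflet practices (64%) and 88 − 36 = 52 of 88 controls (59%). Unadjusted, this adds about 0.05 × 10 points × 0.5 = 0.25 points to the leaflet effect, which a phase 2 term in the model removes.

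**Precision.** The standard error rises by √(180/69) = 1.62 under restriction.

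| Leaflet, 5 points at 6 months, 50% of controls screened by then | Effect (points) | SE (points) | Power |
|---|---|---|---|
| Later, 33 v 36, no phase 2 | 4.5 | 2.7 | 39% |
| Later, all 92 v 88 | 4.19 | 1.6-1.7 | 71-73% |
| 6 months, all 92 v 88 | 5.0 | 1.7 | 85% |

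The range in the second row covers control rates of 40-60%. The 6-month power is 90% if only 29% of controls are screened by then. If the effect in practices without phase 2 is instead a full 5 points at the later time (4.66 in all practices), power is 46-51% restricted and 80-85% in all 180, over control rates of 30-60%. The ranking is unchanged.

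**Break-even.** The two sets give equal power when dilution reaches 1 − √(69/180) = 38%. That needs phase 2 conversion of about 0.10 + 0.38 × 0.90/0.617 = 0.65 to 0.66, against the planned 0.20.

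**Online booking, 10 points, control rate 30-60%.** 17 v 19 practices: 76-80%. All 97 Manchester practices, effect diluted by 7.0% (61/97 exposed to phase 2): 98-99%.

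**The case against.** A reader might infer that the protocol discards 111 practices, about 62%, from all long-term phase 1 analyses. The documents do not support that. No sentence drops them, sections 3.3.1 and 5.2 carry no such restriction, and the Aberdeen power uses essentially every practice. Restriction is documented for online booking only; for the leaflet it is an inference from section 5.1.1. Nor is the large control group wasted. It is the shared comparator for five phase 2 contrasts, and it lowers dilution in an all-practice analysis too.

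The practices without phase 2 also answer a legitimate question: the effect of phase 1 under usual follow-up. The all-practice estimate averages over a mix of phase 2 strategies particular to this trial. That stands, and is why both should be reported.

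The 7% depends on equal conversion in both phase 1 groups, which is untested. The powers also ignore the baseline-uptake covariate and the balanced allocation. Those refinements should help either set and do not remove a 1.6-fold difference in standard error.

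Finally, section 5.2 leaves detail to a statistical analysis plan that is not shown, and choosing the set could belong there. But the protocol itself fixes a remedy, prints a power for a restricted set and miscounts that set. Those statements need correcting wherever the analysis detail sits.

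**Conclusion.** The point holds, with limits. The protocol is inconsistent about which practices inform long-term phase 1 effects. For online booking it names 63, which agrees neither with the 69 in section 5.1.1 and Figure 2 nor with the 36 of those that lie in Manchester; the 94% then becomes about 76-80%. On the protocol's planning values, restriction avoids a dilution of about 7% (0.3 points on a 5-point effect) while raising the standard error about 1.6-fold. For the leaflet that means about 39% power against about 72% in all practices. The leaflet also lacks a time point between 3 months and the start of phase 2, where all 180 practices are still unexposed and power is about 85%.

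These figures assume two-sided 5%, ICC 0.026, 40 women per practice, a 5-point leaflet effect at 6 months and the 10% and 20% conversion rates. The 3-month primary comparison is unaffected. Which set comes first at 12 and 30 months is partly a choice of target, so this should be corrected but does not undermine the trial.

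**What to change.** 1. Add leaflet uptake just before the second reminder, in all randomised practices, as a secondary endpoint. This matches the 5-month online-booking measure. Section 9.1 already records months post call, so no new data are needed.
2. State that 12- and 30-month phase 1 effects are estimated in all randomised practices, with allocated phase 2 arm as a practice-level factor. Include every woman in the phase 1 cohort, not only those still unscreened at 6 months, because selecting on that would break the phase 1 randomisation. Report the practices without phase 2 alongside, as the estimate under usual follow-up, and use a phase 1 by any-phase-2 term as a check.
3. Reconcile 63 with 69 (36 in Manchester) and restate the 94% for the practices that can inform online booking.

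The cost is wording in the protocol and analysis plan; randomisation and data collection do not change. The price is that the all-practice estimate at 12 and 30 months averages over phase 2 conditions, with about 0.3 points of dilution on a 5-point effect.

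### The 94% long-term power for online booking rests on 63 practices, but only 36 Manchester practices (17 v 19) can make that comparison, giving about 76-80%

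*Protocol*

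**What the plan says.** - Protocol section 5.1.1 warns that phase 2 interventions could distort long-term estimates of the phase 1 effects, and answers with a larger phase 2 control group. For the North West it counts: "Of the 180 practices 111 will receive an intervention in phase 2 of the study whilst 69 will receive no further intervention".
- It then notes that the effect of online booking may build up over follow-up, and continues: "63 Greater Manchester practices will receive no intervention". The next sentence is the power claim: "These will have a power of 94% to detect a 10% increase due to access to online booking". No baseline, significance level, ICC, cluster size or split between arms is given for it.
- Section 5.1.1 also states: "The online booking intervention will be tested in Manchester PCT only". Section 4.1 agrees: "Women living in Manchester PCT will be eligible for the internet booking intervention but not those from Salford, Trafford or Aberdeen".
- Figure 2 in section 5.1.2 cross-tabulates the phase 1 and phase 2 allocations. The first Manchester row, with both pre-leaflet and online booking, reads "Yes Yes 3 4 3 4 2 8 24". The last two entries are 8 phase 2 control practices and a row total of 24.

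**The concern.** Two things do not fit. The count of 63 matches neither the 69 in the preceding paragraph nor Figure 2. And whichever count is used, it is drawn from Greater Manchester as a whole, although practices in Salford and Trafford were never randomised to online booking and cannot contribute to a randomised comparison of it.

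Uptake at 12 and 30 months is a stated outcome (sections 3.5 and 3.6), and the protocol expects online booking to have a cumulative effect. The power figure is what tells a reader how much weight a null long-term result could bear. At 94% a true 10-point effect would be missed 6% of the time. If the real figure is 76-80%, it would be missed 20-24% of the time.

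**Working it through.** **Practice counts (Figure 2, control column)**
- Manchester with online booking: 8 + 9 = 17.
- Manchester without online booking: 9 + 10 = 19. Manchester total: 36.
- Salford and Trafford: 16 + 17 = 33.
- North West total: 36 + 33 = 69. This agrees with the 69 in the text and not with 63.

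**Inputs**
- ICC 0.026 and 40 women per practice: stated in section 5.1.1 for the 3-month calculations, carried over here as an assumption.
- Two-sided 5% test: assumed, as none is stated for phase 1.
- Baseline uptake 30-50%: assumed. Section 5.1.1 puts initial response below 30%; section 5.1.2 expects at least 50% not to have attended at 6 months.

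**Formula**
- Design effect = 1 + (40 - 1) x 0.026 = 2.014.
- Effective number per arm = practices x 40 / 2.014.
- SE = sqrt[p1(1 - p1)/n1 + p0(1 - p0)/n0]; power = Phi(difference/SE - 1.96).

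**Check against the neighbouring figures (30% baseline)**
- Pre-leaflet, 92 v 88, 5 points: effective n 1827 and 1748; SE 0.01564; Phi(3.197 - 1.96) = 89.2%. Stated: 89%.
- Online booking at 3 months, 49 v 48, 7.5 points: effective n 973 and 953; SE 0.02147; Phi(3.493 - 1.96) = 93.7%. Stated: 93%.

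The method is therefore close to the one the protocol used.

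**Reproducing the 94%: 63 practices split 31 v 32, 10 points**
- Effective n 616 and 636.
- 40% to 50%: SE 0.02799; Phi(3.572 - 1.96) = 94.7%.
- 30% to 40%: SE 0.02684; Phi(3.726 - 1.96) = 96.1%.

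The stated value appears when all 63 practices are treated as a near-even randomised comparison of online booking.

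**What Figure 2 allows: 17 v 19, 10 points**
- Effective n 17 x 40 / 2.014 = 338 and 19 x 40 / 2.014 = 377.
- 30% to 40%: SE = sqrt(0.24/338 + 0.21/377) = 0.0356; Phi(2.809 - 1.96) = 80%.
- 40% to 50%: SE = sqrt(0.25/338 + 0.24/377) = 0.0371; Phi(2.695 - 1.96) = 77%.
- 50% to 60%: SE = sqrt(0.24/338 + 0.25/377) = 0.0371; Phi(2.698 - 1.96) = 77%.
- A pooled-variance version gives 80.1%, 77.9%, 76.7%, 76.2% and 76.6% at baselines of 30, 35, 40, 45 and 50%. Hence about 76-80%.
- A t-test on 17 + 19 - 2 = 34 degrees of freedom gives 74-78%.
- With a cluster-size coefficient of variation of 0.5, the design effect is 1 + (1.25 x 40 - 1) x 0.026 = 2.274 and power is 71-75%.
- To reach 94% with 17 v 19, the true increase would have to be about 13 points.

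**Other readings of the sentence**
- Practices with no intervention in either phase: this leaves no online booking practices to compare.
- Adding the 33 Salford and Trafford controls to the non-booking side (17 v 52): about 89-92% at baselines of 30-50%. It uses 69 practices, not 63, and is confounded with PCT.
- All 97 Manchester practices (49 v 48): SE 0.0216 to 0.0227, power above 99%. This is not the basis stated.

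**The case against.** The strongest reply is about weight. Section 3.5 makes 3-month uptake the primary endpoint for online booking, and the 93% power for it reproduces. The 94% supports a supplementary remark, sets neither the sample size nor the allocation, and feeds no decision rule. Nothing says a null long-term result will be read through it. Section 5.1.1 also leaves open handling the phase 2 influence by statistical analysis, in which case the comparison need not be confined to 36 practices. All of that stands and limits the severity. It does not rescue the sentence, which bases its figure on practices with no intervention and on a number that fits no table.

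A second reply is that the replacement figure rests on inputs not stated for this sentence. That is right, and is why it is given as a range with its assumptions.

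A reader might extend the point to Aberdeen. For that cohort section 5.1.1 says: "The primary outcome would be the absolute increase in screening uptake by 3, 12 and 30 months compared to control". It then gives power above 95%, while Figure 2 leaves only 15 + 13 = 28 Aberdeen practices without a phase 2 intervention. The documents do not support that extension. The Aberdeen statement names its own basis, 38 v 39 practices, on which the power is about 98%. Nothing confines that comparison to phase 2 controls, and the count of 69 concerns the 180 North West practices only.

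**Conclusion.** The sentence is wrong as written. The count of 63 contradicts the 69 in the same section and in Figure 2, and the 94% needs a split of about 31 v 32 that cannot exist when only 17 Manchester practices have online booking and no phase 2 intervention. With 17 v 19 the power for a 10-point increase is about 76-80%, assuming ICC 0.026, 40 women per practice, a two-sided 5% test and a baseline of 30-50%. It is lower with a t-test or variable cluster sizes.

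This should be fixed, but it is not a defect in the primary comparison. It would be an over-reading to conclude that the trial is underpowered for online booking: the 3-month calculation is sound, and an analysis of all Manchester practices would have high nominal power for the long-term effect.

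**What to change.** Replace 63 with the Figure 2 counts, and restate the long-term power for 17 v 19 Manchester practices as about 76-80%, giving the baseline, significance level, ICC and cluster size used. The sponsor should recompute with its own chosen inputs. The cost is one sentence and a less favourable figure.

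If the 12- and 30-month analysis is meant to use all 97 Manchester practices adjusted for phase 2 arm, the protocol should say so and quote that power instead: about 99% for an undiluted 10-point effect. Two cautions belong with it:
- The estimate is an average over the phase 2 arms, and a covariate for arm does not remove any change that phase 2 makes to the booking effect.
- Section 3.3.4 lets the nurse navigator facilitate internet booking. In Figure 2, 4 + 3 + 2 + 3 = 12 of the 48 Manchester practices without online booking are in the navigator or navigator-choice arms, so the contrast may be diluted and the real power lower.
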